Design	Randomized two-arm clinical trial comparing a personalized exercise program (Intervention Arm – Group 1) to the standard of care (Control Arm – Group 2: Delayed Intervention Group) in patients with lung cancer (primary stage I-IIIa or secondary)
Study Duration	4 years + duration of COVID-19 adjustments
Study Center(s)	Single center - Huntsman Cancer Institute
Objectives	
Primary: Evaluate the improvement in mobility performance via the 6 Minute Walk (6MW) test
 
Secondary:
 
 1. Evaluate the improvement in strength, endurance, and balance via the Short Physical Performance Battery (SPPB) test. 2. Gather patient-reported outcomes regarding disease specific symptoms, multidimensional fatigue, common mental health issues, and hypothesized treatment mechanisms, via questionnaires
Number of Subjects	Randomized clinical trial: 200 (approximately 106 men and 94 women), and 300 approached (anticipated recruitment rate 65%)

Diagnosis and Main Eligibility Criteria
	
Inclusion:
 
 • Male or female subject aged ≥ 18 years. • Suspected (per the treating physician) diagnosis of primary lung cancer stage I, II, or IIIa OR secondary lung cancer. • Disease amenable to surgical resection to be performed at the Huntsman Cancer Hospital in the opinion of the treating surgeon. • Patients must be able to follow directions and complete questionnaires and exercise diaries in English. • Patients must agree to be randomly assigned to either Intervention or Control Group. 
Exclusion:
 
 • Deemed ineligible for surgery by the enrolling physician
	
 • Abnormalities on screening physical exam judged by study physicians or physical therapist to contra-indicate participation in exercise program compliance. • Alcohol or drug abuse as judged by study physicians. • Significant mental or emotional problems that would interfere with study participation, or as assessed by the NCCN Distress Thermometer. Any value higher than 7 on the NCCN Distress Thermometer will trigger further assessment, but ultimately enrollment into the clinical trial will be determined by the enrolling physician.

Study Product, Dose, Route, Regimen and Duration
	
A personalized exercise regimen based on a patient's AM-PAC score and performed in the outpatient setting starting 2 weeks or more pre-surgery, inpatient for the duration of the hospital stay, and outpatient for approximately 6 months post-surgery.

Statistical Methodology
	
Primary analysis
 
Power calculations are based on the group effect in an analysis of covariance for the 6MW test at 8 weeks, with baseline 6MW test as covariate. The planned sample size (n = 200) allows for a 25% drop out rate leaving at least 150 subjects evaluable for the primary endpoint. The hypothesis is that the difference in the 6MW distance between the study arms (Intervention vs. Control) will be ≥ 39.95 m. This effect size stems from a meta-analysis where 4 weeks of post-surgery exercise training provided a 39.95 increase in the 6MW distance in NSCLC patients. Consistent with Arbane, SD = 100 m and correlation = 0.5 between repeated 6MW test measurements on the same subject are assumed. Power to detect the treatment effect was estimated by simulation (in R) of an analysis of covariance model with 6MW test at 2 months post-surgery as outcome, treatment group as primary predictor and pretreatment 6MW test as covariate. Pre and post 6MW test was assumed to be bivariate normally distributed.
 
Secondary analyses
 
See section 10 for details.

------------------------------------	--

1 OBJECTIVES

This study is designed to establish whether participation in a personalized exercise program during the pre- and post-operative setting can positively affect physical performance, cardiorespiratory fitness, quality of life, clinical outcomes (hospital length-of stay and readmission rate, complications), and treatment-related costs in patients undergoing surgery for the treatment of stage I-IIIa NSCLC as well as secondary lung cancer when compared to the current standard of care (no exercise program).

1.1 Primary Objective

1.1.1 Evaluate the improvement in mobility performance.

Primary Endpoint: Six Minute Walk (6MW) distance.

1.2 Secondary Objectives

1.2.1 Evaluate the improvement in strength, endurance, and balance.

Secondary Endpoint #1: Short Physical Performance Battery (SPPB) test scores

1.2.2 Gather patient-reported outcomes regarding disease-specific symptoms, multidimensional fatigue, common mental health issues, and hypothesized treatment mechanisms and evaluate differences between arms.

Secondary Endpoint #2: results from PROMIS, FACT-L (Functional Assessment of Cancer Therapy-Lung), FACIT-F (Chronic Illness Fatigue Scale), PSQI (Pittsburgh Sleep Quality Index), BREQ-3 (Behavioral Regulation in Exercise Questionnaire 3), AM-PAC outpatient short form, activity/exercise, tobacco history, mDES, WHI emotions, loneliness, and Subjective Social Status Ladders questionnaires.

Further secondary endpoints to be explored include self-efficacy, social support, disease-related symptoms (e.g., pain, shortness of breath, fatigue), activities of daily life, personal habits, emotions, exercise diaries, demographics, 7-day physical activity recall, background information, diet (measured by the DHQII from the NCI), cancer treatment distress (CTXD) and living conditions.

1.3 Exploratory Objectives

1.3.1 Evaluate changes in biomarker levels, smoking status, microbiome, and body measurements.

Exploratory Endpoint #1: potential prognostic or mechanistic biomarkers, such as inflammatory biomarkers, in serum, plasma, and buffy coat, possible variations in weight and body measurements over the course of the study. Additionally, smoking status post-surgery and microbiome will be assessed.

1.3.2 Evaluate the rate of complications.

Exploratory Endpoint #2: rate of occurrence of pulmonary, cardiac, and other complications requiring treatment (e.g., liver dysfunction, gastric ulcer, wound infection, colitis, depression), readmissions and deaths within the first 30 days after discharge, death and/or hospitalization due to COVID-19 during or after study.

1.3.3 Measure the length of stay post-surgical resection.

Exploratory Endpoint #3: time from surgery to discharge obtained from clinical databases.

1.3.4 Evaluate costs of the PEP intervention on health care utilization and costs from admission to discharge, from discharge to 2 months follow-up, and from 2 to 6 months follow-up.

Exploratory Endpoint #4: total cost of care and utilization for each of the three periods collected through the UUHS VDO, the Utah APCD, the health care utilization questionnaires, the financial strain (COST) questionnaire, and time-line follow-back.

1.3.5 Assess impact of COVID-19 on the study and participants.

Exploratory Endpoint #5: COVID-19 questionnaire.

1.4.2 Analysis of whether the 6 minute walk (6MW) distance may be predicted based on previous 6MW tests completed.

Exploratory Aim #2: Completed 6MW tests.

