9.3 Exploratory Objectives

Data gathered from all patients who received the PEP intervention and pertaining to the quality of the intervention, participation in the intervention, and attitudes toward exercise (obtained via questionnaires) will be analyzed.

Additionally, the effects of the PEP intervention on the following will be evaluated by comparison between each arm of the study:

- Rate of complications (pulmonary and cardiac events, other complications requiring treatment [e.g., liver dysfunction, gastric ulcer, wound infection, colitis, depression], readmissions, and deaths within the first 30 days after discharge).
- Length of stay post-surgical intervention.
- Death and/or hospitalization post-study relating to COVID-19.

Finally, the effects of the PEP intervention on the following will be evaluated by comparison between each arm of the study:

- Total cost of care and utilization (obtained through the UUHS VDO, the Utah APCD, the health care utilization questionnaires, the financial strain (COST) questionnaire and time-line follow-back).
- Levels of potential prognostic or mechanistic biomarkers such as inflammatory biomarkers, in serum, plasma, and buffy coat. Additionally, smoking status post-surgery and microbiome will be assessed.

- Assess the impact of the Coronavirus (COVID-19) on the study and its participants during the outbreak. A limited dataset (including first name, email address, zip code and study ID) may be shared with IRB_00140849 'Exemption Umbrella Protocol- HCI projects to facilitate a larger review of the impact of COVID-19 on all patient populations listed in the umbrella protocol.

Additional Exploratory Objectives:

- Comparison of paired 6 minute walk tests completed by the same patients in clinic and remotely. Prediction of in clinic 6 minute walk test from remote 6 minute walk test of the same patient.
- Prediction of missing 6MW from completed 6MW and other covariates.

The following information will be abstracted from each participant's medical record to allow the UUHS VDO and Utah APCD staff to provide information on the total cost of care and utilization. It has been required by the UUHS VDO staff that the protocol outlines the specific medical record information before they will provide their services. However, any additional medical record information not already outlined below may also be used by study staff.

- Demographics:
 - Age at time of first clinic visit
 - Date of birth
 - Gender
 - Body Mass Index

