 - weight
 - Patient's Zip Code (to help with calculation of distance to Huntsman)
 - Race: Caucasian, Black, Hispanic, Asian, Native American, Other
 - Zubrod Performance Scale
 - 0 = Normal activity, no symptoms
 - 1 = Symptoms but fully ambulatory
 - 2 = Symptoms but in bed less than 50% of the time
 - 3 = Symptoms but in bed >50% but less than 100%
 - 4 = Bedridden
 - 5 = Moribund
- Risk Factors for complications (Yes/No answers)
 - Weight loss in past 3 months greater than 3 kgs (captured in questionnaire)
 - Infection at the time of initial clinic visit (e.g., pneumonia)
 - Co-morbidities
 - Hypertension
 - Steroid use
 - Congestive Heart Failure

- Coronary Artery Disease
 - Peripheral Vascular Disease
 - Preoperative Chemotherapy
 - Preoperative Radiation therapy
 - Prior Cardiothoracic Surgery
 - History of Stroke
 - Diabetes
 - Renal insufficiency history (documented history of renal failure and/or a history of creatinine value > 2.0)
 - Other co-morbidity not listed above
- Tobacco Use
 - Use of smokeless tobacco
 - Cigarette use
 - Pack Years (no. of packs per day x no. of years smoking)
 - Tobacco Pipe
 - Tobacco Other
- Status of Tobacco Use History
 - Never Smoker
 - Active smoker at time of clinic visit (this patient will be classified for our paper eventually as a recent quitter, as we have a policy of not operating on those who continue to smoke)
 - Quit smoking >12 months before surgery (remote smoker)
- Pulmonary Function Tests
 - Forced Expiratory Volume in 1 second (FEV1): Value and % predicted
 - Diffusion Capacity (DLCO): Value and % predicted
- Outcomes
 - Procedure Type (VATS [either traditional or robot] OR Thoracotomy)
 - Amount of Lung Resection (Wedge Resection, Segmentectomy, Lobectomy, OR Pneumonectomy)
 - Inpatient AMPAC Score at time of discharge
 - Complications postoperatively
 - Pneumonia
 - Air Leak greater than 5 days
 - Adult Respiratory Distress Syndrome (ARDS)
 - Pulmonary Embolus
 - Initial ventilator support >48 hours in the postoperative period
 - Reintubation
 - Tracheostomy
 - Cardiac arrhythmias
 - Bleeding
 - Neurological Event
 - Renal Event
 - Chylothorax

- Wound Infection
 - Other Infection
 - Length of Inpatient Stay
 - Lung Cancer Pathology Description
 - Primary or Secondary
 - If Primary, Lung Cancer Stage
 - Discharge Date
 - Discharge Location (Home, Skilled Nursing Facility, Rehab facility)
 - Readmission within first 30 days after discharge (to Hospital)
 - Additional Therapy after Surgery

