10.3 Primary Endpoint Analysis

Analyses will include all patients that are evaluable for our primary endpoint (expected at least $n=150$). The primary outcome will be the group effect for an analysis of covariance model with 6MW test at 2 months post-surgery as outcome and pretreatment 6MW test as covariate, tested at the nominal two-sided 0.05 significance level. A sensitivity analysis will be performed with additional adjustment variables (listed as covariates in Section 10.1). Missing data will be handled using multivariate imputation by chained equations⁸⁸ as implemented in the R package “mice”.

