10.4 Other Endpoint Analyses

The approach to testing for group differences for each continuous outcome (e.g., quality of life and fatigue summary scales, length of stay after surgical resection, cost) will be to test for the group effect in an analysis of covariance model with adjustment for covariates listed in Section 10.1 as well as baseline values of the outcome variable when available.

Cost data and utilization data are typically positively skewed with some patients having very high costs/utilization. To reflect the distributions of cost and utilization, a generalized linear regression (GLM) with log link and gamma distribution and the generalized beta of the second kind (GB2) will be applied. To examine health care utilization, a Negative Binomial Regression (NBR) will be used to handle over dispersion of patient visits.

The proportion of patients who continue to smoke post-surgery is expected to be too small to include as a reliable adjustment variable or outcome ($\sim 5\%$).⁸⁹ Former smokers will be tested (saliva) at the 6 month clinic visit to assess smoking recidivism. A separate descriptive analysis will be performed in the subset of smokers.

An analogous approach will be used for endpoints coded as binary variables (complications, readmission) using logistic regression models instead of analysis of

covariance models. If diagnostics plots show significant deviation from model assumptions, then a separate sensitivity analysis will be performed using appropriate robust regression methods such as those available in the “robust base” package in R.

The study design provides 96% power to detect a 10 point increase in FACT-L in the Intervention Group compared to the Control Group, similar to the effect of aerobic training on FACT-L reported in Jones.⁴⁶

Bland-Altman analysis will be used to analyze agreement between remote and in clinic 6MW and for calculation of 95% confidence intervals on limits of agreement. The intra-class correlation coefficient will also be reported. Gaussian linear regression models will be used to determine whether remote 6MW and other covariates listed in Section 10 can be used to predict in clinic 6MW. Cross-validation will be used to evaluate performance.

Gaussian linear regression models will be used to assess the ability to predict 6MW from covariates listed in Section 10.1 and previous 6MW. Cross-validation will be used to assess the performance.

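### As worded, the exploratory death component leaves out non-COVID deaths in hospital after surgery, and the plan gives no readmission or length-of-stay rule for those patients

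*Combined protocol and SAP*

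**What the plan says.** Section 1.3.2 defines Exploratory Endpoint #2 as the rate of complications requiring treatment, together with "readmissions and deaths within the first 30 days after discharge". The same sentence adds "death and/or hospitalization due to COVID-19 during or after study", which is not tied to discharge. Section 9.3 repeats the main window for the between-arm comparison: "readmissions, and deaths within the first 30 days after discharge".

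Exploratory Endpoint #3 (section 1.3.3), length of stay, is "time from surgery to discharge obtained from clinical databases".

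The abstraction list in section 9.3 includes in-hospital postoperative complications, length of inpatient stay, discharge date, and readmission within 30 days of discharge. It also has "Discharge Location (Home, Skilled Nursing Facility, Rehab facility", that is, three live destinations and no category for death. Date of death is not on the list, although section 9.3 allows other medical-record data to be used.

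For analysis, section 10.4 says the approach for continuous outcomes such as "length of stay after surgical resection, cost) will be to test for the group effect in an analysis of covariance model". It handles "endpoints coded as binary variables (complications, readmission) using logistic regression models"; death is not named there. Section 10.3 says "Missing data will be handled using multivariate imputation by chained equations", under the primary endpoint analysis. Section 14.4 has deaths on study reported to the IRB, whether related to participation or not.

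**The concern.** The death window opens at discharge, and a patient who dies in hospital after resection is never discharged alive. Followed as written, the between-arm death component passes over such a patient, although the trial is about recovery from surgery and section 2.2 cites mortality risk as part of its rationale.

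Two neighbouring endpoints share the gap. A 30-day readmission is possible only for someone who left hospital alive, but section 10.4 does not limit the readmission model to those patients, so an in-hospital death would be coded as the favourable outcome. Length of stay runs to discharge, and the plan does not say what value, if any, a patient who died receives.

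At stake is whether the exploratory safety and recovery results can be read at face value. If the rule is left open, it will be chosen once the deaths, and possibly their arms, are known.

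**Working it through.** The plan states no figure to reproduce here, so the check is mainly a comparison of definitions, followed by arithmetic on scale.

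**1. Where a non-COVID death in hospital is counted**

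| Place in the plan | Is the death captured? |
|---|---|
| Endpoint #2 and section 9.3, death component | No: the window starts at discharge |
| Endpoint #2, COVID-19 clause | No: the cause is not COVID-19 |
| Section 9.3, postoperative complications | Possibly as a complication, not as a death |
| Section 9.3, discharge location | No category for it |
| Section 10.4, readmission model | Stays in the denominator as not readmitted, unless excluded |
| Section 10.4, length-of-stay model | No rule stated |
| Section 14.4, IRB reporting | Yes, but as safety reporting, not as a between-arm endpoint |

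**2. How many patients.** The planned sample is 200 (section 3.2), here taken as all reaching surgery. In-hospital mortality *p* is not given, so it is an assumption. Expected deaths = 200 × *p*; probability of at least one = 1 − (1 − *p*)^200.

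| Assumed *p* | Expected deaths | P(at least one) |
|---|---|---|
| 0.5% | 1 | 0.633 |
| 1% | 2 | 0.866 |
| 2% | 4 | 0.982 |
| 3% | 6 | 0.998 |

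Across this range the rule is more likely than not to be needed, but for only a handful of patients.

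**3. Effect on readmission.** With 1:1 allocation there are 100 patients per arm. If *k* patients in an arm die in hospital and are kept as not readmitted, the proportion computed is the proportion among live discharges multiplied by (100 − *k*)/100. For *k* = 2 the factor is 98/100 = 0.98, a relative reduction of 2%.

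**4. Effect on length of stay.** Assume a mean stay of 7.5 days in survivors, the midpoint of the 5 to 10 days in section 8.4, and suppose a death on day *d* is entered as a discharge on that day. The shift in the arm's mean is *k*(*d* − 7.5)/100.

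- Two deaths on day 3: 2 × (3 − 7.5)/100 = −0.09 day.
- Two deaths on day 30: 2 × (30 − 7.5)/100 = +0.45 day.

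The shift is small, and its sign depends on when the deaths occur.

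**5. Where the window closes.** With stays of 5 to 10 days, 30 days after discharge falls between day 5 + 30 = 35 and day 10 + 30 = 40 after surgery. This is a spread between patients; nothing in the documents shows a difference between arms.

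**The case against.** The strongest reply is that these deaths do not disappear. COVID-19 deaths are counted during or after the study under section 1.3.2, section 14.4 has deaths on study reported to the IRB, and many fatal courses would register as one of the abstracted complications. All of that stands. A reader might infer that the trial counts deaths only after discharge, or that in-hospital deaths go unrecorded; the documents support neither. None of these routes, however, puts a non-COVID in-hospital death into the between-arm death component.

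A second reply is that the wording may simply give the end of follow-up, without meaning to exclude earlier deaths, since the abstraction list attaches the 30-day window to readmission alone. That is possible. But sections 1.3.2 and 9.3 both attach it to deaths, and no passage says that earlier deaths are included.

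Third, a clinical database may hold a discharge date for a patient who died, and the abstraction list has a separate field for length of stay. This also stands: what is missing is a stated rule, and the documents do not show that the value itself would be absent.

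Finally, the endpoints are exploratory, sections 10.2 to 10.4 attach no power claim to them, and so few deaths could not support a mortality comparison under any window. That limits the weight of the point but does not make the definition right.

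**Conclusion.** The point holds in a limited form. On the literal wording of sections 1.3.2 and 9.3, non-COVID deaths in hospital after surgery fall outside the between-arm death component. The readmission model would treat such patients as successes if they are left in, and length of stay has no rule for them.

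The size is modest: 1 to 6 of 200 patients on an assumed mortality of 0.5% to 3%, for which the documents offer no anchor. A reader might infer that the length-of-stay comparison is biased in favour of the arm with more early deaths. The documents do not support that as a general conclusion: on the assumed figures, two deaths move one arm's mean by −0.09 to +0.45 day, in either direction, and whether a death would be entered as a discharge at all is unknown. Nor do they show that the two arms' windows would close at different times.

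The primary 6MW analysis is unaffected. The correction is worth making because it is cheap and because the rule should be set before outcomes by arm are seen.

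**What to change.** 1. In sections 1.3.2 and 9.3, count all deaths from the day of surgery, including those in hospital, to one fixed post-surgery day in both arms. A day no earlier than day 40 would keep every death the current window covers for stays of up to 10 days. Name the analysis for deaths in section 10.4; with so few events, counts by arm would do.
2. Keep the 30-day post-discharge window for readmission, and restrict that analysis to patients discharged alive. This conditions on a post-randomisation event, so show the deaths by arm beside it.
3. In the section 9.3 abstraction list, add date of death and a died-in-hospital category under discharge location.
4. In section 10.4, state that a death before discharge is not entered as a completed stay. The planned analysis of covariance can remain for patients discharged alive, with a sensitivity analysis giving in-hospital deaths the worst rank. A competing-event analysis is another reasonable choice, but is not required.

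The cost is a wording change in three sections, one added data field with its new category, and a small extra analysis. Section 9.3 already permits additional medical-record data, and deaths on study are already reported. Sample size and the primary analysis do not change.

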2.5 Rationale for Conducting the Study

Studies that have investigated the effect of exercise in lung cancer patients undergoing surgery have been center-based and resource intensive, and consequently have not been implemented in the clinical setting.⁶⁵⁻⁶⁷ Pre-operatively, effective exercise programs lasting 6-12 weeks are not feasible since patients with lung cancer do not want to delay surgery. In fact, one randomized controlled trial (RCT)³⁸ was prematurely discontinued because neither patients nor providers were willing to delay surgery longer than 4 weeks. Post-surgery, home-based exercise strategies capable of improving mobility and fatigue levels of patients following surgery for lung cancer and colorectal cancer⁴⁵ have been prohibitively expensive because they required supervised visits by a nurse.³² In addition, these programs have been “one size fits all,” lacking a personalized approach to optimize adherence and efficacy.⁶⁵⁻⁶⁸

To date, no attempt has been made to test a pragmatic and personalized exercise intervention (i.e., face to face visits at clinical contacts, telephone counseling in the home, and personalized exercise prescriptions) before and following surgery for patients with lung cancer. Unfortunately, the application of personalized principles of exercise in randomized controlled trials with cancer survivors (specifically non-breast cancer survivors) is incomplete and inconsistent.⁶⁹ To establish consistency in the exercise prescription while accommodating the exercise to match the patient’s level of mobility, a validated basic mobility assessment tool to create modes and dosages of exercise that can be implemented across the continuum of the pre- and post-operative surgical experience in lung cancer patients may prove to be beneficial. The Activity Measure-Post Acute Care™ (AM-PAC) (described in Figure 2) will be used as the basic mobility assessment tool that prompts the prescribed exercise mode and dose for the patient. The AM-PAC has been developed as a pragmatic measurement system that can be used across care settings and a very broad range of impairments, limitations and diagnoses.⁷⁰ The PEP Study’s approach with the use of AMPAC will address a gap in the care of lung cancer patients, i.e., the underutilization of exercise because it is clinically not pragmatic and it is not known how and when to implement exercise.⁷¹

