8 STUDY PROCEDURES

8.1 Pre-Surgery Clinic Visit

During their pre-surgery clinic visit (which typically takes place 2-4 weeks prior to surgery as long as surgery is not delayed), all potential lung cancer patients who are surgical candidates (as determined and approved by the surgeon) will be approached about the PEP study. Enrollment may be postponed, and the decision to do so is dependent on all three principal investigators' discretion. This visit may be completed 1 week or up to 6 months prior to surgery depending on the health of the patient and surgical policies. This window may increase if patient and surgical policies require it. Patients who are interested and potentially eligible will undergo the following procedures either in the clinic space or at the Population Sciences (HOPE) clinic located in HCI Research North. All procedures listed below can, as is practical and applicable, also be performed by the study team and participants via telephone, text, email, snail mail, and/or MyChart:

- Informed consent. Consenting may be performed remotely, via phone, video chat, mail and/or email in situations where study staff is unable to consent in person. A copy of the signed consent form may be mailed or emailed to the participant. The process for consenting when unable to do so in person will include the following:
 - A brief introduction of the study from the treating surgeon.
 - Study staff will be notified of the potential participant from the treating surgeon or their clinic staff.
 - The research staff will attempt to contact the potential participant by phone to introduce the study. An email, text message, or message through MyChart may be sent if the patient does not answer.
 - Once the potential participant is reached by phone, the research team will discuss the study and email, mail, or send the consent form via MyChart if the patient is interested.
 - The patient will be given directions to sign the consent form (either personally or electronically) and email the signed copy back to study staff. Study staff will sign then sign the consent form upon receipt.
 - A copy of the signed consent form will be emailed, mailed, or sent through MyChart to the participant.
 - Study staff will coordinate a day and time to meet with the participant to perform study procedures that are required in person. Any procedures that may be completed remotely can be completed before the scheduled date and time.

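### The cost comparison opens at hospital admission, so the pre-surgery part of PEP, delivered to Group 1 only, is left out, and no source is named for PEP's own delivery cost

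*Combined protocol and SAP*

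**What the plan says.** Section 1.3.4 defines the cost objective over three periods: "Evaluate costs of the PEP intervention on health care utilization and costs from admission to discharge, from discharge to 2 months follow-up", with the third running from 2 to 6 months. Exploratory Endpoint #4 is the "total cost of care and utilization for each of the three periods collected through the UUHS VDO, the Utah APCD, the health care utilization questionnaires", with the COST questionnaire and time-line follow-back as further sources. Section 9.3 repeats the sources and lists the financial fields to be abstracted: service dates, visit indicators, a physical therapy indicator, charge amount, and diagnosis and procedure codes. Section 10.4 models cost with a gamma GLM with log link and a GB2 model, and visits with negative binomial regression. It has no step that adds the cost of delivering PEP.

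The synopsis has PEP "performed in the outpatient setting starting 2 weeks or more pre-surgery", continuing in hospital and then "outpatient for approximately 6 months post-surgery". Section 8.1 puts randomisation and the first PEP session at the pre-surgery visit, typically 2-4 weeks ahead, and allows a wide margin: "This visit may be completed 1 week or up to 6 months prior to surgery". At that visit Group 1 receives individual therapist instruction, the exercise packet and the activity tracker. Group 2 receives a welcome letter, a factsheet and a team introduction. Section 8.2 adds weekly calls for Group 1 until surgery.

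**The concern.** The cost window opens after the intervention has started. Whatever the data sources contain, a resource used between randomisation and admission cannot enter any of the three periods. In that interval PEP uses therapist time, staff calls and materials that Group 2 does not receive.

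The question is not incidental to the protocol. Section 1 lists treatment-related costs among the outcomes on which PEP is to be compared with standard care. Section 2.5 describes earlier home-based programmes as "prohibitively expensive because they required supervised visits by a nurse", and section 2.7 presents an added physical therapist as the one extra resource PEP needs. If that resource is partly or wholly uncosted, a result of no added cost or of savings would not answer the question the rationale raises. More patients would not remove the omission, because it is systematic.

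**Working it through.** The plan gives no unit cost, cost SD or cost effect size, so there is no figure of its own to reproduce. The check compares the two timelines and then sizes what falls outside the window.

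**Inputs from the documents**
- Lead time before surgery: 2-4 weeks typical, 1 week to 6 months allowed (8.1).
- PEP after surgery: about 6 months, taken as 26 weeks (synopsis).
- PEP sessions with the therapist: pre-surgery, 2 months and 6 months (section 6), each about 30-40 minutes, or 0.50-0.67 h (5.2).
- Calls: weekly before surgery and during follow-up (8.2, 8.6).
- Evaluable sample: 150, or 75 per arm (10.2; used only for the last step).

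**Assumptions (not in the documents)**
- 15 minutes (0.25 h) per call and $60-120 per staff hour.

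**Share of PEP before surgery** = lead weeks / (lead weeks + 26)
- 2 weeks: 2/28 = 7.1%
- 4 weeks: 4/30 = 13.3%
- 1 week: 1/27 = 3.7%
- 26 weeks (the 6-month extreme): 26/52 = 50%
- Scheduled therapist PEP sessions: 1 of 3. The initial packet and tracker are issued entirely before surgery.

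**Staff time that the window excludes, typical lead**
- Low: 2 calls x 0.25 h + 0.50 h = 1.0 h; at $60 per hour, $60.
- High: 4 calls x 0.25 h + 0.67 h = 1.67 h; at $120 per hour, $200.
- Materials are additional.

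**Staff time over the whole programme** (relevant only if the sources hold no delivery cost at all)
- Calls: (2 to 4) + 26 = 28-30; x 0.25 h = 7.0-7.5 h.
- Sessions: 3 x (0.50 to 0.67 h) = 1.5-2.0 h.
- Total: 8.5-9.5 h; at $60-120 per hour, $510-1,140, plus materials.
- These are scheduled counts. Calls may be fewer, since 5.2.2 and 8.2 allow missed or less frequent calls. Therapist time may be greater, since inpatient supervision (5.2.1) and the discharge review of exercises (8.5) are not counted.

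**Sensitivity to the assumptions.** Take therapist time at $50-150 per hour, calls of 10-30 minutes at $30-100 per hour, and materials at $50-200.
- Pre-surgery, low: 0.5 x 50 + 2 x (10/60) x 30 + 50 = $85.
- Pre-surgery, high: (40/60) x 150 + 4 x 0.5 x 100 + 200 = $500.
- Whole programme, low: 3 x 0.5 x 50 + 28 x (10/60) x 30 + 50 = $265.
- Whole programme, high: 3 x (40/60) x 150 + 30 x 0.5 x 100 + 200 = $2,000.

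**Direction.** Let D be the true mean difference in total cost, Group 1 minus Group 2, and d > 0 the omitted mean delivery cost per Group 1 patient. With no matching delivery in Group 2 over the interval, the comparison estimates D - d.

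**Scale against sampling error.** SE = SD x sqrt(2/75). For an assumed cost SD of $10,000, SE = $1,633; for $30,000, SE = $4,899.

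**The case against.** The strongest reply is that this is the fourth of several exploratory endpoints and can be read as downstream cost: section 9.3 speaks of PEP's effects on total cost of care and utilisation. Downstream cost is a legitimate quantity if it is labelled as such. The plan does not label it, and both the opening words of 1.3.4 and the aims in Section 1 suggest something wider. This reply supports clearer labelling. It does not justify leaving the text as it is.

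A second reply is that the omission is small. That stands for precision: $60-200 plus materials is well below the illustrative standard errors. It is still a shift of known sign that can be costed directly from counts.

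Three stronger readings are tempting, and the documents do not support them.
- A reader might infer that half of PEP is left out. That holds only at the 6-month extreme.
- A reader might infer that the sources hold none of PEP's delivery cost. The abstracted fields include a physical therapy indicator, charges and procedure codes, and 9.3 allows further medical record data. The documents do not say whether study sessions are billed, so the $510-1,140 cannot be presented as the established omission.
- A reader might infer that everything excluded favours PEP. The window also drops ordinary pre-admission care in both arms, and its net direction is unknown.

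The cost rationale should not be overstated either. Section 2.3 offers financial and resource demands only as a possible reason for low uptake; section 2.5 is the plain statement.

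**Conclusion.** The concern holds in a limited form. From the text alone, the cost comparison excludes PEP's start-up in Group 1: the first therapist session, the packet, the tracker and the pre-surgery calls. On the typical timeline this is about 7-13% of programme duration and 1 of 3 scheduled therapist PEP sessions, or about 1.0-1.7 staff hours. In money it is about $60-200 plus materials, resting on the assumed call length and hourly rate; the share grows with longer lead times.

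Post-surgery delivery cost may also be missing. That is a plausible inference from the sources and fields listed, not an established fact. The direction, a lower Group 1 minus Group 2 difference, is certain only for delivery cost.

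Primary and secondary conclusions are unaffected. This is a cheap improvement to an exploratory endpoint, and it bears on any claim that PEP saves money or adds no cost.

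**What to change.** - In 1.3.4 and Exploratory Endpoint #4, add a period from randomisation to admission and a total from randomisation to the 6-month follow-up. Carry the same wording into 9.3.
- Cost Group 1 delivery from session and call records (number and duration) and materials issued, at stated unit costs. State whether study sessions are billed, and count any billed session only once.
- In 10.4, report the between-arm cost comparison both with and without delivery cost. Label the version without it as downstream cost only, and state that it cannot by itself support a cost-saving claim.

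The cost is wording in three sections, an earlier start date for the data pull (service dates are already among the requested fields) and a small costing exercise from study records. The downside is a less favourable cost figure for PEP.
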